APPENDIX 2. PARTIAL DATE CONVENTIONS

Imputed dates will NOT be presented in the listings.

ALGORITHMS OF PARTIAL DATES FOR AEs AND MEDICATIONS

Partial dates for AEs and medications will be imputed as follows:

Adverse event or prior/concomitant medication start date (references to year and month refer to the year and month of the start date, respectively):

1. If year and month are known, and it is the month of the first dose date and the stop date is prior to the first dose date, use the first day of the month.
2. If year and month are known, and it is the month of the first dose date and the stop date is the same as or later than the first dose date, use the first dose date.
3. If year and month are known, and it is the month following the first dose date, use the first day of the month.
4. If year and month are known and it is any month prior to first dose date, use the first day of the month.
5. If only year is known, and it is previous to the year of the first dose date, use June 30th of that year. If it is the same as first dose date year, assume it is the first dose date. If it is later than the first dose date year, assume it is the first day of the year.
6. If the start date is completely missing, use the first dose date.
7. Should any of the previous start dates created be after a complete stop date provided, use the stop date instead of the date that would otherwise be created.
8. Otherwise, if start date is unknown leave as missing.

Adverse event or prior/concomitant medication stop date (references to year and month refer to the year and month of the stop date, respectively):

1. If year and month are known and study medication stopped during that month, use the stop date of study medication.
2. If year and month are known and study medication stopped after that month, use the last day of the month.
3. If year and month are known and study medication stopped prior to that month, use the first day of the month.
4. If only year is known, and it is the same as last dose date year, assume it is the last dose date. If it precedes the last dose date year, assume it is the last day of the year. If it is later than the last dose date year, assume it is the first day of the year.
5. If stop date is unknown and continuing is checked, set to date of last double-blind dose.
6. Should any of the previous stop dates created come before a start date, either a complete date or an imputed one, use the start date instead of the date that would otherwise be created.
7. Otherwise, if stop date is unknown leave as missing.

ALGORITHM FOR PARTIAL DATES IN MEDICAL HISTORY

Partial dates for medical history (including psychiatric history) will be imputed as follows:

Document:	K:\DSP\SM-13496\RVA97109\Biostatistics\Documentation\SAP	Version Number:	1.0
Author:	[REDACTED]	Version Date:	20MAR2018

Template No: CS_TP_BS016 – Revision 3
Effective Date: 01May2012

Reference: CS_WI_BS005

Copyright © 2012 [REDACTED]. All rights reserved.
The contents of this document are confidential and proprietary to [REDACTED]. Unauthorized use, disclosure or reproduction is strictly prohibited.

Medical history start date (references to year and month refer to the year and month of the start date, respectively):

1. If year and month are known, and it is the year or month previous to Screening, use the last day of the month.
2. If year and month are known, and it is the month of Screening, use Screening date – 1.
3. If only year is known, and it is previous to the year of Screening, use June 30th of that year.
4. If only year is known, and it is the year of Screening, use Screening date – 1.

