6. GENERAL CONSIDERATIONS

6.1. REFERENCE START DATE AND STUDY DAY

Study Day will be calculated from the reference start date, and will be used to show start/ stop day of assessments and events.

Reference start date is defined as the day of the first dose of study medication, (Day 1 is the day of the first dose of study medication of the long-term study).

- If the date of the event is on or after the reference start date then:

Study Day = (date of event – reference start date) + 1.

- If the date of the event is prior to the reference start date then:

Document: K:\DSP\SM-13496\RVA97109\Biostatistics\Documentation\SAP

Author: [REDACTED]

Version Number: 1.0

Version Date: 20MAR2018

Template No: CS_TP_BS016 – Revision 3

Reference: CS_WI_BS005

Effective Date: 01May2012

Copyright © 2012 [REDACTED] All rights reserved.

The contents of this document are confidential and proprietary to [REDACTED].
reproduction is strictly prohibited.

[REDACTED] Unauthorized use, disclosure or

Study Day = (date of event – reference start date).

In the situation where the event date is partial or missing, the date will appear partial or missing in the listings, and Study Day, and any corresponding durations will be presented based on the imputations specified in Appendix 2: Partial Date Conventions.

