17.1. ADVERSE EVENTS

Adverse Events (AEs) will be coded using Medical Dictionary for Regulatory Activities (MedDRA) central coding dictionary, Version 19.1. All categories of AEs will be summarized by treatment group for the safety population.

Listings will be provided of TEAEs resulting in death, serious TEAEs, and TEAEs resulting in discontinuation from the study. All three listings will use the safety population.

Treatment-emergent adverse events (TEAEs) are defined relative to Week 28 and Week 52 as follows:

- TEAEs up to Week 28 defined as:

Document:	K:\DSP\SM-13496\RVA97109\Biostatistics\Documentation\SAP	Version Number:	1.0
Author:	[REDACTED]	Version Date:	20MAR2018

Template No: CS_TP_BS016 – Revision 3
Effective Date: 01May2012

Reference: CS_WI_BS005

Copyright © 2012 [REDACTED] All rights reserved.
The contents of this document are confidential and proprietary to [REDACTED]. Unauthorized use, disclosure or reproduction is strictly prohibited.

- o AEs with a start date on or after the date of first dose of study medication through 7 days after last dose of study medication (14 days for serious adverse events and deaths) for subjects outside Japan, or
- o Subjects within Japan who early terminate the study prior to Week 28 will be derived based on the derivation above
- o For subjects within Japan who participate in the study after Week 28, TEAEs will include AEs with a start date on or after the first dose of study medication up to Week 28
- TEAEs up to Week 52 defined as:
 - o AEs with a start date on or after the date of first dose of study medication through 7 days after last dose of study medication (14 days for serious adverse events and deaths) for all subjects within Japan

All AEs with an onset date after the consent date for the long-term study but prior to the first dose in the long-term study will be summarized separately in the long-term study. Adverse events and serious adverse events (SAEs) with completely missing onset dates will be summarized as treatment emergent regardless of severity or relationship to study medication, unless the AE stop date occurs before the date of first dose of study medication.

See Appendix 2 for handling of partial dates for AEs. In the case where it is not possible to define an AE as treatment emergent or not, the AE will be classified by the worst case; i.e. treatment emergent.

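### Stop-date rule 5 in SAP Appendix 2 ties continuing adverse events and medications to a prior-study dose date (minor)

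*SAP*

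**What the plan says.** SAP Appendix 2 gives seven rules for the stop date of an adverse event or medication. Rules 1 to 4 handle partial dates and refer to the end of study medication; rule 1, for example, says that if "study medication stopped during that month, use the stop date of study medication". Rule 5 covers a record marked as continuing: "If stop date is unknown and continuing is checked, set to date of last double-blind dose". Rule 6 is a floor: should an imputed stop "come before a start date, either a complete date or an imputed one, use the start date". Rule 7 is the fallback: "Otherwise, if stop date is unknown leave as missing".

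The imputations feed output. SAP 6.1 says that Study Day "will be used to show start/ stop day of assessments and events" and that, where a date is partial or missing, Study Day and "any corresponding durations will be presented based on the imputations specified in Appendix 2: Partial Date Conventions". SAP 17.1 adds: "Listings will be provided of TEAEs resulting in death, serious TEAEs, and TEAEs resulting in discontinuation from the study".

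**The concern.** SAP 3.1 describes D1002002 as open-label. SAP 2.1, 3.3 and 6.2 apply the term double-blind to D1002001, and nothing in either document gives it another meaning for this study. Rule 5 is thus the only stop rule that points outside the study, and it breaks with the four rules above it.

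For completers, the last double-blind dose should fall at or just before Day 1. This is inferred: SAP 6.2 sets the long-term baseline at Week 6 of D1002001, and Protocol 3.3 starts dosing on the day of the baseline visit. An event that is still unresolved would then receive a stop day that says the opposite. New recruits, by SAP 3.3, had no treatment assignment in D1002001, so the rule cannot be applied to them, and the two cohorts are handled differently for no stated reason.

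What is at stake is the reading of individual records. In the listings of serious events and of events leading to discontinuation, an unresolved event could appear to have ended on the day it began.

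**Working it through.** The plan gives no figure to reproduce, so the check applies the stop rules as written and then again with the last D1002002 dose as the anchor.

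**From the documents**
- Study Day (SAP 6.1): date − first dose + 1 on or after first dose; date − first dose before it.
- Stop date (Appendix 2, rules 5 and 6): the later of the anchor and the start date.
- Visit windows (Protocol Tables 1 to 3): Week 28, Days 188 to 204; Week 52, Days 356 to 372.
- Follow-up visit (Protocol 3.2.1): 14 ± 7 days after completion or discontinuation.

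**Assumed**
- First long-term dose 15 March 2015 (Day 1), last double-blind dose 14 March (Day −1), last long-term dose 27 September (196 days after first dose, so Day 197).
- Duration = stop − start + 1, because the SAP states no duration formula for adverse events.

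**Example 1: completer, continuing event with onset 10 May.** Onset is 56 days after first dose, so Day 57.
- As written: the anchor is Day −1, which precedes onset. Rule 6 moves the stop to Day 57. Duration 57 − 57 + 1 = 1 day.
- Last long-term dose as anchor: 197 − 57 + 1 = 141 days.

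**Example 2: completer, continuing record that began 1 February.** The start is 42 days before first dose, so Day −42.
- As written: stop on 14 March, Day −1. Duration 41 + 1 = 42 days.
- Last long-term dose as anchor: 42 + 196 + 1 = 239 days.

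**Example 3: new recruit.** There is no anchor, so rule 7 leaves the stop missing.

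**Sensitivity to the assumed dates**

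| Varied | As written | Last long-term dose as anchor |
|---|---|---|
| Onset Day 57, last dose Day 188 to 204 | 1 day | 132 to 148 days |
| Onset Day 57, last dose Day 356 to 372 | 1 day | 300 to 316 days |
| Start 1 February, last double-blind dose 0 to 7 days before Day 1 | 43 down to 36 days | 239 days |

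The first two rows take the last dose on the visit day. In the third row the stop as written is 196 to 203 days earlier than with the other anchor.

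The last-dose anchor is not the true end either. If the event in Example 1 is still continuing at the follow-up visit, timed here at 7 to 21 days after last dose, it has lasted at least 141 + 7 = 148 to 141 + 21 = 162 days.

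**Could a treatment-emergent event be lost?** SAP 17.1 defines treatment emergence by start date. Start rule 1 moves an event dated only to the month of first dose back to the first of that month if its stop precedes first dose. A stop imputed by rule 5 could trigger this, but only if stops were imputed before starts. The SAP states no order. However, start rule 7 deals with an imputed start that would "be after a complete stop date provided, use the stop date instead of the date that would otherwise be created", while stop rule 6 allows the start to be imputed. That wording implies starts come first. Start rules 1 and 2 then have no stop to test, start rule 8 leaves the date missing, and the worst-case rule in SAP 17.1 keeps the event as treatment-emergent.

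**The case against.** The strongest reply is that little of this reaches a reader. Appendix 2 opens by stating that imputed dates are not listed, and SAP 6.1 keeps a missing date missing in the listings. SAP Appendix 1 asks for all collected case report form variables to be listed, and Protocol 6.3.1.3 records an outcome for each event, including not resolved. A 1-day duration would therefore sit beside a blank stop date and a contradicting outcome. The listing templates are not in the documents, so it is unknown whether stop day or duration is shown. SAP 17.1 plans no summary of event duration. SAP 13 classes a medication as concomitant if it was ongoing at the end of the study, with no stop date needed. For new recruits, a missing stop on a continuing record is close to the right handling.

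Most of this stands as a limit on consequence, and it is why the point is minor. It does not remove the error. Under SAP 6.1 the date stays blank while Study Day and duration are still presented from the imputation, so the wrong value can appear without the date that would explain it. A programmer may well see the phrase as a leftover and correct it, but that would be an undocumented departure from the plan.

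**Conclusion.** The concern holds, and it is minor. Stop rule 5 is wrong as written. For completers of D1002001, a continuing record that began on study gets a stop day equal to its onset and a duration of 1 day, and one that began earlier is dated as ended around or before Day 1. For new recruits the rule has no date to use.

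The 1-day result for on-study onsets does not depend on the assumed calendar dates, provided the last double-blind dose is no later than onset. The 141-day comparison and the ranges in the table do depend on them; they illustrate the mechanism and do not estimate impact. The number of affected records is not in the documents.

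The demonstrated effect is confined to derived stop days and durations, and it is visible only if the outputs show them. Efficacy endpoints, concomitant status and planned incidence tables are not shown to change, and SAP 17 plans no comparison of safety between groups.

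**What to change.** Replace stop rule 5 in SAP Appendix 2 with wording such as:

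> A record with an unknown stop date that is marked as continuing is treated as ongoing; where a date is needed, use the date of last dose of study medication in D1002002, or the start date if that is later.

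Apply it to completers and new recruits alike. Add one sentence saying that a continuing record dated only to the month of first dose falls under start rule 2, which settles the order-of-imputation question. The last-dose date should be understood as a convention in line with stop rules 1 to 4, not as the true end of an ongoing event.

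The cost is two sentences in Appendix 2, with no new data.

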APPENDIX 3. MEDICAL REVIEW OF TERMS

EPS Terms	Metabolic Terms	Combined Terms	Treatment Emergent Mania Terms	Mood Event Terms
Muscle rigidity	Blood cholesterol increased	Parkinsonism: Muscle rigidity, Bradykinesia, Parkinsonism, Tremor, Psychomotor retardation	Bipolar disorder	Disease progression
Trismus	Blood glucose increased		Euphoric mood	Apathy
Bradykinesia	Blood insulin increased		Hypomania	Bipolar disorder
Dystonia	Blood triglycerides increased		Mania	Depression
Parkinsonism	Fructosamine increased			Euphoric mood
Tremor	Glucose urine present			Hypomania
Psychomotor retardation	High density lipoprotein decreased	Dystonia: Dystonia, Trismus		Intentional self-injury
	Lipids abnormal	Somnolence: Hypersomnia, Sedation, Somnolence		Listless
	Low density lipoprotein increased			Mania
	Weight increased			Self-injurious ideation
	Diabetes mellitus			Suicidal ideation
	Dyslipidaemia			Suicide attempt
	Glucose tolerance impaired			
	Hypercholesterolaemia			
	Hyperglycaemia			
	Hyperinsulinaemia			
	Hyperlipidaemia			
	Hypertriglyceridaemia			
	Metabolic disorder			

Document: K:\DSP\SM-13496\RVA97109\Biostatistics\Documentation\SAP
 Author: [Redacted] Version Number: 1.0
 Version Date: 20MAR2018

Template No: CS_TP_BS016 – Revision 3 Reference: CS_WI_BS005
 Effective Date: 01May2012

Copyright © 2012 [Redacted] All rights reserved.
 The contents of this document are confidential and proprietary to [Redacted]. Unauthorized use, disclosure or reproduction is strictly prohibited.

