3.4.2 Safety variables

- Incidence of adverse events (AEs) and adverse drug reactions (ADRs)
- Incidence of extrapyramidal AEs and ADRs
- Proportion of patients with concomitant use of antiparkinson medication

- Change from baseline in the prior study (D1002001) and the present study (D1002002) in the Drug-Induced Extrapyramidal Symptoms Scale (DIEPSS) total score (except for the overall severity score) at the final assessment and at each assessment point
- Change from baseline in the prior study and the present study in the individual DIEPSS symptoms scores at the final assessment and at each assessment
- Change from baseline in the prior study and the present study in the serum prolactin concentration at the final assessment and at each assessment point
- Change from baseline in the prior study and the present study in the ECG parameter (QTc) at the final measurement
- Change from baseline in the prior study and the present study in the fasting blood glucose, HbA1c (NGSP), glycoalbumin, total cholesterol, LDL cholesterol, HDL cholesterol and triglycerides at the final measurement
- Change from baseline in the prior study and the present study in the body weight at the final measurement
- Laboratory measures and vital signs
- Proportion of patients with any instance of suicide attempt or suicidal ideation based on the Columbia Suicide Severity Rating Scale (C-SSRS)

Rationale

Extrapyramidal symptoms are the most common side effects associated with antipsychotics and usually treated with antiparkinson drugs. The DIEPSS²²⁾ is an evaluation scale for the extrapyramidal symptoms that are caused by drugs.

Antipsychotics are known to increase serum prolactin concentration²³⁾. Some atypical antipsychotics are known to influence glucose metabolism, lipid metabolism, and body weight. Some drugs affect cardiac rhythm (eg, QT interval prolongation).

The rate of suicide is high for bipolar disorder, and prevention of suicide is one of the important aspects in the treatment of bipolar disorder. The C-SSRS²⁴⁾ is a tool designed to systematically assess and track suicidal adverse events (suicidal attempts and suicidal ideation), and is able to comprehensively identify suicidal events while limiting the over-identification of suicidal behavior.

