6.3.1.2 Objective findings

Clinically significant abnormal objective findings (eg, clinical laboratory value, ECG value, and physical examination observation) will also be recorded as AEs.

When a clear diagnosis is available that explains the objective findings, this diagnosis will be recorded as the AE, and not the abnormal objective finding (eg, viral hepatitis will be recorded as the AE, not transaminase elevation). If a definite diagnosis is not available, then record the sign (eg, clinically significant elevation of transaminase levels) or symptom (eg, abdominal pain) as the AE.

Clinical laboratory test results will be reviewed by the investigator. The investigator should determine the clinical significance of all out of range values. Clinical laboratory test with possibly drug-related or clinically relevant abnormal values of uncertain causality may be repeated. Any abnormal values that persist should be followed at the investigator's discretion.

All on-site ECG tracings and ECG reports by the ECG parameter measurement center

will be reviewed by the investigator. The investigator should determine the clinical significance of all abnormal ECGs. ECG with possibly drug-related or clinically relevant abnormal findings of uncertain causality may be repeated. Any abnormal ECGs that persist should be followed at the investigator's discretion.

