6.3.2 Laboratory tests

Blood and urine samples for the laboratory tests will be collected at Visits 0 (only for Japanese patients who did not participate in the prior study), 1, 4, 6, 8, 10, 12, 14 and 16 and at discontinuation, and will be submitted to the central laboratory for analysis. At Visit 10 (outside Japan) or 16 (in Japan) or at discontinuation, the samples should be collected within 72 hours after the final administration of the study drug and before the post treatment with antipsychotics. All blood samples will be collected in a fasting condition. Collection and handling of blood samples will be performed in accordance with the routine procedures and the separately provided instructions.

The central laboratory will analyze the samples for the tests listed in Table 8.

Table 8 Contents of the laboratory variables

Hematology	Red blood cell count, white blood cell count, hemoglobin, hematocrit, platelet count, differential white blood cell
Blood Biochemistry	AST, ALT, ALP, γ -GTP, total protein, total bilirubin, BUN, creatinine, total cholesterol, LDL cholesterol, HDL cholesterol, triglycerides, LDH, CK, fasting blood glucose ^{a)} , uric acid, HbA1c, glycoalbumin, prolactin, albumin, insulin, electrolytes (Na, K, Cl)
Endocrine	Thyroid stimulating hormone (TSH), free thyroxine (FT4), total and free testosterone
Hepatitis ^{b)}	HBs antigen, HCV antibody (Low positive HCV antibody will be confirmed by INNO-LIA method.)
Urinalysis (qualitative tests)	Protein, glucose, urobilinogen, occult blood

a) Fasting condition will not be mandatory at screening for patients who did not participate in the prior study.

b) Hepatitis tests will be performed only at screening for patients who did not participate in the prior study.

A pregnancy test (urine chorionic gonadotropin) will be performed in female patients of childbearing potential before menopause at the study site at Visits 0 (only for Japanese patients who did not participate in the prior study) or 1 (for completers of the prior study), Visits 4, 6, 8, 10, 12, 14 and 16, and at discontinuation. If urine pregnancy test is positive, serum pregnancy test will be performed.

Total and free testosterone will be measured only in male patients.

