2.2. SAFETY OBJECTIVES

The following safety objectives will be analyzed throughout the study up to Week 28 outside Japan and Week 52 within Japan, unless otherwise specified:

- 1) Incidence of adverse events (AEs) and adverse drug reactions (ADRs)
- 2) Incidence of extrapyramidal AEs and ADRs
- 3) Proportion of subjects with concomitant use of antiparkinson medication
- 4) Change from baseline in the prior double-blind study (D1002001) and the present study (D1002002):
 - Drug-Induced Extrapyramidal Symptoms Scale (DIEPSS) total scores (except for the overall severity score)

Document:	K:\DSP\SM-13496\RVA97109\Biostatistics\Documentation\SAP	Version Number:	1.0
Author:	[REDACTED]	Version Date:	20MAR2018

Template No: CS_TP_BS016 – Revision 3
Effective Date: 01May2012

Reference: CS_WI_BS005

Copyright © 2012 [REDACTED] All rights reserved.
The contents of this document are confidential and proprietary to [REDACTED]. Unauthorized use, disclosure or reproduction is strictly prohibited.

- DIEPPS individual symptoms scores
 - Serum prolactin concentration
 - ECG parameter (QTc)
 - Fasting blood glucose, HbA1c (NGSP), glycoalbumin, total cholesterol, LDL cholesterol, HDL cholesterol and triglycerides
 - Body weight (kg)
- 5) Laboratory measures and vital signs
- 6) Proportion of subjects with any instance of suicide attempt or suicidal ideation based on the Columbia-Suicide Severity Rating Scale (C-SSRS)

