17.1.5.2. Metabolic TEAEs

The overall incidence of Metabolic TEAEs will be summarized by Preferred Term and treatment group. These will be identified by using a list of specified terms from medical personnel, which can be found in Appendix 3. This summary will be repeated for all Japanese subjects up to Week 52 separately as well.

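### The Appendix 3 list that defines metabolic TEAEs has no term for raised HbA1c, so a subject with only that event would not be counted

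*SAP*

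**What the plan says.** Under adverse events of special interest, SAP 17.1.5.2 states: "The overall incidence of Metabolic TEAEs will be summarized by Preferred Term and treatment group". It then gives the rule for picking out the events: "These will be identified by using a list of specified terms from medical personnel, which can be found in Appendix 3". The section names no standardised query, makes no provision for similar terms and describes no later update. The table is repeated for Japanese subjects up to Week 52.

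The Metabolic Terms column of Appendix 3 has 19 entries. Ten are findings and nine are diagnoses or disorders. One of the findings is "Fructosamine increased". None names HbA1c or glycated haemoglobin.

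Protocol 3.4.2 lists among the safety variables the change from baseline in "fasting blood glucose, HbA1c (NGSP), glycoalbumin, total cholesterol, LDL cholesterol, HDL cholesterol and triglycerides at the final measurement", and SAP 2.2 repeats the same seven laboratory variables. Protocol Table 8 puts HbA1c among the central laboratory tests ("uric acid, HbA1c, glycoalbumin, prolactin"). SAP Table C gives HbA1c a markedly abnormal limit of 7.5% or higher.

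Protocol 6.3.1.2 explains how a laboratory value becomes an adverse event: "Clinically significant abnormal objective findings (eg, clinical laboratory value, ECG value, and physical examination observation) will also be recorded as AEs". If a clear diagnosis explains the value, the diagnosis is recorded. Otherwise: "If a definite diagnosis is not available, then record the sign".

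**The concern.** The term list is the whole definition of the metabolic category, so anything not on it cannot enter the incidence. The list does not set out to exclude laboratory findings, since more than half of it consists of findings. In several places it pairs a finding with its diagnosis, as with raised glucose and hyperglycaemia, or raised triglycerides and hypertriglyceridaemia. Against that pattern the absence of HbA1c looks like an oversight, and the SAP gives no reason for it.

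Metabolic effects are a stated safety interest. The protocol's background names weight and glucose effects of other available drugs, and the rationale in 3.4.2 notes that some atypical antipsychotics affect glucose, lipids and weight. With treatment lasting 28 or 52 weeks, HbA1c is a natural glycaemic marker to follow. A missing term can only lower the reported incidence, never raise it.

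**Working it through.** The plan states no metabolic TEAE rate, so there is no figure to reproduce. The check sets the list beside the variables it might be expected to cover.

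| Variable | Named in protocol 3.4.2 | Measured | Markedly abnormal limit in SAP | Finding term in Appendix 3 |
|---|---|---|---|---|
| Glucose | yes | Table 8 | Table C | yes |
| HbA1c | yes | Table 8 | Table C | **none** |
| Glycoalbumin | yes | Table 8 | none | none by name; coding unknown |
| Total cholesterol | yes | Table 8 | Table C | yes |
| LDL cholesterol | yes | Table 8 | Table C | yes |
| HDL cholesterol | yes | Table 8 | none | yes |
| Triglycerides | yes | Table 8 | Table C | yes |
| Body weight | yes | vital signs | Table E | yes |
| Insulin | no | Table 8 | none | yes |
| Fructosamine | no | not in Table 8 | none | yes |

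1. **Coverage.** Of the seven metabolic laboratory variables in protocol 3.4.2, five have a direct finding term. Five of the seven also have a Table C limit (glucose, HbA1c, total cholesterol, LDL, triglycerides), and HbA1c is the only one of those five without a term.

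2. **Is the gap an artefact of the text?** The blood and urine findings run alphabetically. Nothing stands between the urine glucose entry and the HDL entry, where a term beginning with glycosylated haemoglobin would fall.

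3. **Can the missed event arise?** It needs four things: a raised HbA1c after baseline; a judgement by the investigator that it is clinically significant; no diagnosis to record in its place; and no other listed metabolic TEAE in that subject. The schedule allows the first. Protocol 6.3.2 has laboratory samples at Visits 4, 6, 8 and 10 outside Japan (4 post-baseline samples) and also at Visits 12, 14 and 16 in Japan (7 samples). Protocol 6.3.1.2 allows the second and third. If diabetes mellitus, hyperglycaemia or impaired glucose tolerance is recorded instead, the subject is counted, because all three are listed.

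4. **Size per missed subject.** The formula is 1 divided by the number in the safety population. Assume, for illustration, that this equals the enrolment target.
   - All subjects: 325 + 80 = 405, and 1/405 = 0.25 percentage points. Five such subjects would give 5/405 = 1.2 points.
   - Subjects who did not take part in the prior study: 1/80 = 1.25 points.

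   The number of missed subjects is not given and cannot be derived, so no total or relative undercount follows.

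**The case against.** The strongest case on the other side has four parts.

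**HbA1c is well reported elsewhere.** It has observed values, changes and shifts from both baselines (SAP 17.3), subgroup summaries (17.3.3) and a markedly abnormal count (Table C). An HbA1c adverse event keeps its own row in the general table by system organ class and preferred term (17.1.1). All of this stands, so no reader should infer that the HbA1c signal is hidden. It does not repair the grouped figure. Adding the HbA1c row to the metabolic total gives only an upper bound, because a subject may have several terms. The Table C count also uses a fixed threshold instead of the investigator's judgement.

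**The protocol does not ask for this table.** Protocol 9.6.1 requires no metabolic adverse event summary, and no passage says the list must mirror 3.4.2. That is true, and it limits the weight of the point. But once the SAP reports a metabolic incidence as a result of special interest, its definition should fit the variables the plan itself treats as metabolic.

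**The list may come from events already reported.** The SAP is dated 20 March 2018, after planned enrolment closed in February 2017. If the column held only terms that had occurred, a missing HbA1c term would mean that no such event existed. The SAP does not say this. Section 17.1.7.3 ties medical review of coded terms before lock to the combined terms only. A term for fructosamine, which is not a study test, points more to a generic list. That is a pointer and not proof, because a raised glycoalbumin might be coded there.

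**Nothing is tested.** The study is single-arm with no hypothesis (protocol 9.5.1), and the SAP plans no statistical comparison of safety data. So no decision rule depends on this total.

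**Conclusion.** The gap is real and can be checked from the text: the rule in SAP 17.1.5.2 would leave out a subject whose only metabolic TEAE is raised HbA1c recorded as a finding. The effect is confined to the metabolic TEAE incidence. It is about 0.25 percentage points per such subject among 405, if the safety population meets the target, and more in the smaller prior-treatment groups.

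Three stronger readings are tempting, and the documents do not support them:

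- A reader might infer that the metabolic incidence is in fact too low. The loss is conditional on HbA1c-only events, and if none occurred the figure is unchanged.
- A reader might put a percentage on the undercount. That needs event rates that the documents do not give.
- A reader might treat glycoalbumin as a second proven omission. The documents do not show how a raised value is coded, and it may map to the listed fructosamine term.

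The point is a modest inconsistency that is worth correcting because correction is nearly free.

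**What to change.** Add the coded preferred term for raised HbA1c (glycosylated haemoglobin), in the MedDRA version the SAP names (19.1), to the Metabolic Terms column. If its absence is deliberate, give the reason in Appendix 3 instead.

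Before database lock, check the column against the metabolic variables in protocol 3.4.2 and SAP Table C. As part of that check, establish how a raised glycoalbumin event is coded, and add its term only if it does not already map to a listed one.

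The cost is one or possibly two entries in a list, with no new data and no change of design. The downside is that the reported metabolic incidence may become slightly higher.
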